#### 9.3.1. Solicited Events and Symptoms

Solicited adverse events were collected pre-vaccination, 90 minutes post-vaccination following oral dosing or 30 minutes post-vaccination following SL and ID dosing, and then daily for 7 days after each vaccination and graded on a scale of 0 (none), 1 (mild), 2 (moderate) and 3 (severe). Grading scales for solicited adverse events are presented in [Table 7](#). Systemic events for the oral and sublingual routes include: fever, feverishness, fatigue, malaise, myalgia, or headache. Systemic events for the intradermal route include: fever,

feverishness, fatigue, malaise, myalgia, headache, diarrhea, nausea, vomiting, or abdominal discomfort. Local events for the oral route include: irritation of the oral cavity or tongue, diarrhea, nausea, vomiting, and abdominal discomfort. Local events for the sublingual route include: irritation of the oral cavity or tongue, facial nerve disturbance, diarrhea, nausea, vomiting, or abdominal discomfort. Local events for the intradermal route include: injection site pain, redness, swelling, bruising, itching, hypo/hyper pigmentation and induration, vesicles or hardened mass.

The proportion of participants reporting at least one solicited adverse event will be summarized for each solicited adverse event, any systemic symptom, any local symptom, and any symptoms. The 95% CI calculated using Clopper-Pearson methodology from a binomial distribution (SAS Proc Freq with a binomial option) will be presented (beginning at [Table 97](#) and concluding with [Table 104](#)).

For each systemic and local event, any systemic event, any local event, and any solicited event, the maximum severity over 7 days after each vaccination will be summarized for the Safety population. The number and percentage of participants reporting each event will be summarized by the maximum severity and treatment group, separately for each vaccination and over all vaccinations. For each event the denominator is the number of participants with non-missing data for the specific event (beginning at [Table 105](#) and concluding with [Table 112](#)).

The number of participants reporting a solicited adverse event will be summarized for each day post vaccination for each vaccination and for all vaccinations combined both in a summary table (beginning at [Table 113](#) and concluding with [Table 134](#)) and graphically in a bar chart (beginning at [Figure 238](#) and concluding with [Figure 253](#)). A comparison of the event rate for each treatment group between vaccination 1 and vaccination 2, vaccination 2 and vaccination 3, and vaccination 1 and vaccination 3 will be presented ([Table 135](#), [Table 136](#), and [Table 137](#)).

Solicited adverse events by participant will be presented in Listing [16](#), Listing [17](#), Listing [18](#), Listing [19](#), Listing [20](#), and Listing [21](#).

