9 ASSESSMENT OF SAFETY

9.1 Specification of Safety Parameters

The Investigator is responsible for reporting all AEs that are observed or reported during the study, regardless of their relationship to investigational product or their clinical significance.

All events will be recorded on appropriate clinical report forms with notation of duration, severity, and outcome.

Safety and tolerability will be assessed by the frequency and severity of:

1. Study vaccine-related SAEs occurring from first vaccination through 6 months after the last study vaccination.
2. Solicited AEs – reactogenicity events occurring within 7 days of each dose of vaccine:
 - a. Systemic Reactions to include: feverishness (chills/shivering/sweating), fatigue (tiredness), malaise (general unwell feeling), myalgia (body aches, muscular pain), or headache, diarrhea, nausea, vomiting, or abdominal discomfort. Note: for the oral and SL routes of administration, diarrhea, nausea, vomiting, and abdominal discomfort will be evaluated as local reactions as described below.
 - b. Systemic Reactions to also include the measurement of daily oral temperature
 - c. Local Reactions
 - i. For oral route of administration: irritation of the oral cavity or tongue, plus diarrhea, nausea, vomiting, and abdominal discomfort
 - ii. For SL route of administration: irritation of the oral cavity or tongue, or facial nerve disturbance, plus diarrhea, nausea, vomiting, and abdominal discomfort
 - iii. For ID route of administration: injection site pain, redness, swelling, bruising, itching, hypo/hyper pigmentation and induration, vesicles or hardened mass.
3. Unsolicited AEs – study vaccine-related non-serious AEs from first vaccination through 28 days after the last (third) dose of vaccine

4. Withdrawals and discontinuation of study vaccinations will be assessed as a part of determining tolerability

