#### **4.5.1. Safety Variables**

Safety, reactogenicity, and tolerability will be assessed by:

1. Frequency and Severity of Solicited Adverse Events – reactogenicity events occurring from vaccination through 7 days after each dose of vaccine is administered:
  - a) Local solicited events include: irritation of the oral cavity or tongue, diarrhea, nausea, vomiting, and abdominal discomfort for Oral Cohorts; irritation of the oral cavity or tongue, facial nerve disturbance, diarrhea, nausea, vomiting, or abdominal discomfort for Sublingual Cohorts; and injection site pain, redness, swelling, bruising, itching, hypo/hyper pigmentation and induration, vesicles or hardened mass for Intradermal Cohorts.
  - b) Systemic solicited events include: fever, feverishness, fatigue, malaise, myalgia, or headache for Oral and Sublingual Cohorts; and fever, feverishness, fatigue, malaise, myalgia, headache, diarrhea, nausea, vomiting, or abdominal discomfort for Intradermal Cohorts.
2. Frequency of participant withdrawals from first vaccination through the end of follow-up (Day 209 for Oral and Sublingual Cohorts, Day 223 for Intradermal Cohorts)
3. Frequency of discontinuation of study vaccination during the study

4. Frequency and severity of unsolicited vaccine-related non-serious adverse events (AE), including laboratory AE, from first vaccination through 28 days after the last dose of vaccine is administered (Day 57 for Oral and Sublingual Cohorts, Day 71 for Intradermal Cohorts)
5. Frequency of vaccine-related SAEs from the first vaccination through the end of follow-up (Day 209 for Oral and Sublingual Cohorts, Day 223 for Intradermal Cohorts)

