**Table 90: Correlation of ASC IgG Count vs ALS IgG Titers GMFR by Time Point and Treatment Group, Per Protocol Population**

## 14.3 Safety Data

### 14.3.1 Displays of Adverse Events

**Table 91: Overall Summary of Adverse Events - Oral & Sublingual Cohorts**

	Cohort A: Oral 5 µg dmLT (N=X)		Cohort B: Oral 25 µg dmLT (N=X)		All Oral Cohorts: Placebo (N=X)		All Oral Route Subjects (N=X)		Cohort C: Sublingual 5 µg dmLT (N=X)		Cohort D: Sublingual 25 µg dmLT (N=X)		All Sublingual Cohorts: Placebo (N=X)		All Sublingual Route Subjects (N=X)	
Subjects a with	n	%	n	%	n	%	n	%	n	%	n	%	n	%	n	%
At least one local solicited adverse event	x	x	x	x	x	x	x	x	x	x	x	x	x	x	x	x
At least one systemic solicited adverse event	x	x	x	x	x	x	x	x	x	x	x	x	x	x	x	x
At least one unsolicited adverse event	x	x	x	x	x	x	x	x	x	x	x	x	x	x	x	x
At least one related unsolicited adverse event, through 28 days after the last dose	x	x	x	x	x	x	x	x	x	x	x	x	x	x	x	x
Mild (Grade 1)	x	x	x	x	x	x	x	x	x	x	x	x	x	x	x	x
Moderate (Grade 2)	x	x	x	x	x	x	x	x	x	x	x	x	x	x	x	x
Severe (Grade 3)	x	x	x	x	x	x	x	x	x	x	x	x	x	x	x	x
Not yet assessed																
At least one related unsolicited adverse event, from first vaccination through 6 months after the last dose	x	x	x	x	x	x	x	x	x	x	x	x	x	x	x	x
Mild (Grade 1)	x	x	x	x	x	x	x	x	x	x	x	x	x	x	x	x
Moderate (Grade 2)	x	x	x	x	x	x	x	x	x	x	x	x	x	x	x	x
Severe (Grade 3)	x	x	x	x	x	x	x	x	x	x	x	x	x	x	x	x
Not yet assessed																

	Cohort A: Oral 5 µg dmLT (N=X)		Cohort B: Oral 25 µg dmLT (N=X)		All Oral Cohorts: Placebo (N=X)		All Oral Route Subjects (N=X)		Cohort C: Sublingual 5 µg dmLT (N=X)		Cohort D: Sublingual 25 µg dmLT (N=X)		All Sublingual Cohorts: Placebo (N=X)		All Sublingual Route Subjects (N=X)	
Subjects a with	n	%	n	%	n	%	n	%	n	%	n	%	n	%	n	%
At least one severe (Grade 3) unsolicited adverse event	x	x	x	x	x	x	x	x	x	x	x	x	x	x	x	x
Related	x	x	x	x	x	x	x	x	x	x	x	x	x	x	x	x
Unrelated	x	x	x	x	x	x	x	x	x	x	x	x	x	x	x	x
At least one serious adverse event b	x	x	x	x	x	x	x	x	x	x	x	x	x	x	x	x
At least one related, serious adverse event	x	x	x	x	x	x	x	x	x	x	x	x	x	x	x	x
At least one adverse event leading to early termination c	x	x	x	x	x	x	x	x	x	x	x	x	x	x	x	x
Study withdrawal for any reason	x	x	x	x	x	x	x	x	x	x	x	x	x	x	x	x
Discontinuation of study vaccination for any reason	x	x	x	x	x	x	x	x	x	x	x	x	x	x	x	x

N = Number of subjects in the Safety Population

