**Table 92: Overall Summary of Adverse Events - Intradermal & Pooled Cohorts**

*[Implementation note: Treatment groups are Cohort E: Intradermal 0.3 µg dmLT (N=X), Cohort E: Intradermal Placebo (N=X), and All Intradermal Route Subjects (N=X). All Subjects (N=X) will be added at the end.]*

**Table 93: Adverse Events Occurring in 5% of Subjects in Any Treatment Group by MedDRA System Organ Class and Preferred Term, and Treatment Group – Oral & Sublingual Cohorts**

MedDRA Preferred Term	MedDRA System Organ Class	Cohort A: Oral 5 µg dmLT (N=X)			Cohort B: Oral 25 µg dmLT (N=X)			All Oral Cohorts: Placebo (N=X)			All Oral Route Subjects (N=X)			Cohort C: Sublingual 5 µg dmLT (N=X)			Cohort D: Sublingual 25 µg dmLT (N=X)			All Sublingual Cohorts: Placebo (N=X)			All Sublingual Route Subjects (N=X)						
		n	%	Events	n	%	Events	n	%	Events	n	%	Events	n	%	Events	n	%	Events	n	%	Events	n	%	Events	n	%	Events	
Serious Adverse Events																													
All	All	x	x	x	x	x	x	x	x	x	x	x	x	x	x	x	x	x	x	x	x	x	x	x	x	x	x		
PT1	SOC1	x	x	x	x	x	x	x	x	x	x	x	x	x	x	x	x	x	x	x	x	x	x	x	x	x	x		
Etc.	Etc.																												
Other (Non-serious) Adverse Events																													
All	All	x	x	x	x	x	x	x	x	x	x	x	x	x	x	x	x	x	x	x	x	x	x	x	x	x	x		
PT1	SOC1	x	x	x	x	x	x	x	x	x	x	x	x	x	x	x	x	x	x	x	x	x	x	x	x	x	x		
Etc.	Etc.																												

N = number of subjects in the Safety Population (number of subjects at risk).

n= number of subjects reporting event.

Events= total frequency of events reported.

Tables with similar format:

**Table 94: Adverse Events Occurring in 5% of Subjects in Any Treatment Group by MedDRA System Organ Class and Preferred Term, and Treatment Group – Intradermal & Pooled Cohorts**

*[Implementation note: Treatment groups are Cohort E: Intradermal 0.3 µg dmLT (N=X), Cohort E: Intradermal Placebo (N=X), and All Intradermal Route Subjects (N=X). All Subjects (N=X) will be added at the end.]*

**Table 95: Serious Adverse Events by MedDRA System Organ Class and Preferred Term, and Treatment Group – Oral & Sublingual Cohorts****Table 96: Serious Adverse Events by MedDRA System Organ Class and Preferred Term, and Treatment Group – Intradermal & Pooled Cohorts**

*[Implementation note: Treatment groups are Cohort E: Intradermal 0.3 µg dmLT (N=X), Cohort E: Intradermal Placebo (N=X), and All Intradermal Route Subjects (N=X). All Subjects (N=X) will be added at the end.]*

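### The any-local and any-systemic solicited rows use different symptom lists for intradermal than for oral and sublingual, so comparisons across that line and the pooled cells of SAP Table 92 mix definitions

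*SAP*

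**What the plan says.** SAP 9.3.1 lists solicited symptoms by route. Systemic, oral and sublingual: "Systemic events for the oral and sublingual routes include: fever, feverishness, fatigue, malaise, myalgia, or headache". Systemic, intradermal, as SAP 4.5.1 puts it: "fever, feverishness, fatigue, malaise, myalgia, headache, diarrhea, nausea, vomiting, or abdominal discomfort for Intradermal Cohorts".

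The local lists are also in SAP 9.3.1. For oral dosing: "Local events for the oral route include: irritation of the oral cavity or tongue, diarrhea, nausea, vomiting, and abdominal discomfort". The sublingual list has these five items plus facial nerve disturbance. The intradermal list holds injection-site reactions only, with no GI symptom.

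The split comes from Protocol 9.1: "for the oral and SL routes of administration, diarrhea, nausea, vomiting, and abdominal discomfort will be evaluated as local reactions".

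Table 91 (oral and sublingual) has a row for participants with a local solicited event and the row "At least one systemic solicited adverse event". Table 92 takes the same format for Cohort E, with the instruction "All Subjects (N=X) will be added at the end". The footnotes to Table 91 neither define the two composites nor say that they change with route. Table 135 (dose 1 against dose 2) lists Cohorts A to E under one systemic block and one local block; its footnote covers denominators only.

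Cohort E received two of its three planned doses (SAP 4.4.5 and section 15).

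**The concern.** Under these definitions the same episode of diarrhea is a local event in Cohorts A to D and a systemic event in Cohort E. A reader who sets the any-systemic figure for intradermal against the oral or sublingual figure is comparing different events. The all-subjects cell adds them together.

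This matters because solicited reactogenicity is a primary safety endpoint (Protocol and SAP 3.2.1), and Protocol 2.2.1 names residual enterotoxicity as a possible cause of diarrhea and other GI effects. GI tolerability is what a reader would want to see on one scale for all routes, and the summary rows do not give it.

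**Working it through.** The plan states no expected rate for these composites, so there is no figure to reproduce. The check compares the lists and then illustrates size under stated assumptions.

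**Lists (SAP 9.3.1 and 4.5.1)**

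| Route | Systemic | Local |
|---|---|---|
| Oral | 6, no GI | 5: mouth irritation + 4 GI |
| Sublingual | the same 6 | 6: the oral list + facial nerve disturbance |
| Intradermal | 10: the same 6 + 4 GI | 9 injection-site items, no GI |

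Oral and sublingual have identical systemic lists, and their local lists differ by one item.

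**Effect of list length alone.** Assume every symptom has the same risk p, symptoms are independent, and true reactogenicity is equal in all routes. P(any of k symptoms) = 1 − (1 − p)^k.
- p = 2%: 1 − 0.98^6 = 11.4% (oral/sublingual); 1 − 0.98^10 = 18.3% (intradermal).
- p = 5%: 1 − 0.95^6 = 26.5%; 1 − 0.95^10 = 40.1%.

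**Adding the dose count.** Tables 91-92 have no dose split, so their solicited rows cover three 7-day windows in A to D and two in E. Let p be the three-dose risk, spread evenly and independently over doses. Oral/sublingual then has 6 × 3 = 18 symptom-dose chances and intradermal 10 × 2 = 20, so the intradermal exponent is 20/3.
- p = 2%: 1 − 0.98^(20/3) = 12.6%, against 11.4%. The gap is 1.2 points rather than 6.9.
- p = 5%: 1 − 0.95^(20/3) = 29.0%, against 26.5%. The gap is 2.5 points rather than 13.6.

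**Direction.** Let s be the three-dose risk of any of the six common symptoms and g that of any GI symptom, independent and equal in all routes. Oral/sublingual any-systemic is s. Intradermal over two windows is 1 − [(1 − s)(1 − g)]^(2/3). With s = 20%:
- g = 5%: 1 − 0.76^(2/3) = 16.7%, below 20%.
- g = 20%: 1 − 0.64^(2/3) = 25.7%, above 20%.

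The sign therefore depends on the GI rate, which the documents do not give.

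**Pooled cell.** SAP 4.4.3 plans 12 + 3 per cohort, so Cohorts A to E give 60 oral/sublingual and 15 intradermal participants (actual numbers are not in the SAP). Take s = g = 20% and ignore the missing dose. Intradermal is 1 − 0.8 × 0.8 = 36%, and the pooled rate is (60 × 20% + 15 × 36%)/75 = 23.2%. One common list would give 20% (GI left out everywhere) or 36% (GI counted everywhere); 23.2% is neither. For s of 10-30% and g of 5-40%, the pooled rate lies 0.7 to 7.2 points above the six-symptom rate and 2.8 to 28.8 points below the ten-symptom rate.

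**GI incidence.** Tables 97-112 show each symptom, any systemic, any local and any symptom. GI is combined with mouth irritation (oral), with mouth irritation and facial nerve disturbance (sublingual), or with the six systemic symptoms (intradermal). No row counts participants with at least one GI event. Four symptom counts only place that number between the largest of them and the smaller of their sum and N, because one person may report several.

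**The case against.** The split is prespecified and follows the site of administration. Every summary is descriptive, with no hypothesis test (SAP 6.8), and the primary endpoint specifies no comparison between routes. Intradermal sits in Table 92, apart from Table 91. Tables 97-112 report all four GI symptoms for every group, with separate columns per dose, and their any-symptom row does not depend on the local/systemic label. Table 135 even allows a doses 1-2 figure to be derived for each route-specific composite. Protocol 8.1 does not expect diarrhea or vomiting to be common or severe, so the effect may be small.

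Most of this stands, and it limits the point. It does not rescue the pooled cells: Protocol 11.4.2 asks for solicited summaries by group and does not ask for pooling over routes. Nor does it supply a GI composite. The any-symptom row still includes route-specific items, and Table 135 carries the same mixed definitions. Participant-level GI incidence could be rebuilt from the by-participant Listings 16-21, but from no planned table.

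A reader might infer three stronger things.
- That all route comparisons fail. They do not: oral against sublingual uses the same systemic list and nearly the same local list.
- That intradermal must look worse on systemic events. The two-window calculation shows that this cannot be said, since the shorter follow-up partly offsets the longer list.
- That GI harm is hidden. It is not; each symptom is tabulated.

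**Conclusion.** The point holds for intradermal against oral or sublingual on the any-local and any-systemic rows (Tables 91-92 and 135), and for the pooled local and systemic cells in the all-subjects column of Table 92. Those pooled percentages correspond to no single event.

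The net distortion is unknown in size and direction. For any-systemic, the longer intradermal list and the missing third window pull in opposite directions; under equal, independent risks they leave a gap of 1.2 points at 2% per symptom and 2.5 points at 5%. For any-local, the non-GI items are wholly different by route, so no common rate can sensibly be assumed. All rates here are assumptions, and correlation between symptoms would change them.

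No planned inference changes. This is a reporting fault in a primary safety summary, worth correcting because the correction is nearly free and gives a GI figure that the tables otherwise lack.

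**What to change.** 1. Keep the route-specific tables as they are.
2. In Table 92, remove the local and systemic solicited cells from the all-subjects column.
3. In Tables 91-92, add two rows defined identically for every route: any GI solicited event (diarrhea, nausea, vomiting, abdominal discomfort) and any of the six common systemic symptoms. Show each for any dose and for doses 1-2, so that one version has the same number of windows in Cohorts A to E. Pool only these rows.
4. Footnote the route-specific local and systemic definitions under Tables 91-92 and 135-137.
5. Do not add an administration-site composite to any cross-route or pooled display. Its items would differ by route, and facial nerve disturbance is solicited only for sublingual.

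The cost is four added rows in each of two tables (two composites, two dose windows), two cells removed, and footnotes under five tables. The symptoms are already collected and graded one by one, so no new data are needed.

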### 9.3.2. Unsolicited Adverse Events

The proportion of participants reporting at least one unsolicited adverse event will be summarized by MedDRA system organ class and preferred term and treatment group for each vaccination and over all vaccinations. Denominators for percentages are the number of participants who received the vaccination being summarized.

Unsolicited adverse events by participant will be presented in Listing [22](#).

The following summaries for unsolicited adverse events will be presented by MedDRA system organ class, preferred term, vaccination and treatment group:

- Participant listing of non-serious adverse events of moderate or greater severity ([Table 139](#));

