4 STUDY DESIGN

This is an outpatient Phase 1 double-blinded, placebo-controlled, dose-escalation trial in approximately 135 (plus any additional participants if needed to have minimal evaluable participants / cohort as described in [Table 1](#)) apparently healthy adult volunteers, age 18-45 years, who meet all the eligibility criteria and reside in Bangladesh, an endemic country for ETEC infection. The study population will be recruited from Mirpur, a densely populated urban slum community of Dhaka, Bangladesh, known as having a high rate of diarrheal, respiratory and enteric disease.

This clinical trial is designed to assess the safety, reactogenicity, tolerability, and immunogenicity of a range of dosages of dmLT administered by three different routes: oral, SL, or ID. The schematic of study design is presented in [Table 1](#). The oral and SL routes of administration will evaluate dosages of 5, 25, and 50 μ g of dmLT; the ID route of administration will evaluate dosages of 0.3, 1.0, and 2.0 μ g of dmLT. Participants will receive a total of three sequential doses of dmLT; the oral and SL routes will be at days 1, 15, and 29 and the ID route will be at days 1, 22, and 43. After each dose of study product, participants will be observed for 30-90 minutes, depending on the route of administration.

Safety, reactogenicity, and tolerability of the study products will be evaluated for each participant. Solicited local and systemic reactogenicity will be collected for 7 days after each vaccine administration. Memory Aids and digital thermometers will be given to participants to record solicited local and systemic reactogenicity including elevated body temperature (i.e., fever) at home, and they will be reviewed with the participants. Unsolicited AEs will be collected from the time of each study vaccination through 28 days after the last vaccination. Safety laboratories will be collected on Visit 7 or about 28 days after the last vaccination. Serious adverse events (SAEs) will be collected from the time of the first study vaccination through 6 months after the last study vaccination. Tolerability of the study products will be assessed by recording the occurrence of and reason for study withdrawals and discontinuation of study vaccination during the study.

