7.3.2 VISIT 3 - Second Vaccination (~14 days post dose 1 ±2 days)

- This visit is ~14 days after the first dose for oral and SL cohorts and ~21 days after the first dose for the ID cohorts (window ± 2 days)
- Confirm ongoing consent and review eligibility criteria with the participant prior to performing any study procedures, to include updating the medical history and concomitant medications
- Record oral temperature, pulse, and blood pressure
- Targeted physical examination, if indicated based on review of medical history
- Collect approximately 6 mL of venous blood:
 - 2 mL for serum ELISA and neutralization assays
 - 2 mL for ASC assay
 - 2 mL for ALS assay
- Collect stool (approximately 4 gm) and saliva (approximately 2 mL)
- 1-2 gm of stool frozen at $-80^{\circ}\text{C} \pm 15^{\circ}\text{C}$ for future use microbiome studies
- Urine pregnancy test for all women will be performed and must be negative prior to dosing. Provide instructions to women participants to avoid pregnancy through the 28 days from receipt of the last dose of vaccine.
- Perform pre-vaccination reactogenicity assessment
- Administer vaccine dose 2, per the randomization code and observing the required pre-vaccination fasting for oral and rinsing for SL dosing
- Provide memory aid and other 7-day solicited AE and reactogenicity instructions
- Ask participant if they still have the digital thermometer for recording daily oral temperature for seven days following administration of the study product and offer re-instruction on the use of the thermometer as needed.
- Perform post-vaccination reactogenicity assessment after 90 minutes for oral cohorts and after 30 minutes for SL and ID cohorts. This assessment is to include unsolicited AEs and SAEs.
- Provide stool sample collection container and instructions on how to collect stool sample
- Confirm date and time for Visit 4

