#### **4.4.5. Selection and Timing of Dose for Each Subject**

Cohort A and B participants received 3 doses administered orally in clinic on Day 1, Day 15, and Day 29. Cohort C and Cohort D received 3 doses administered sublingually in clinic on Day 1, Day 15, and Day 29. Cohort E participants received 2 doses administered intradermally in clinic on Day 1, Day 22.

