**Listing 22: 16.2.7.3: Unsolicited Adverse Events**

Adverse Event	Associated with Dose No.	No. of Days Post Associated Dose (Duration)	Severity	SAE?	Relationship to Study Treatment	In Not Related, Alternative Etiology	Action Taken with Study Treatment	Subject Discontinued Due to AE	Outcome	MedDRA System Organ Class	MedDRA Preferred Term
Treatment Group: , Subject ID: , AE Number:											
Comments:											
Treatment Group: , Subject ID: , AE Number:											
Comments:											
Note: For additional details about SAEs, see Table 122.											

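### SAP 9.3.2 gives unsolicited AE percentages per vaccination with no common window: for oral and sublingual cohorts, dose 3 has about twice the observation time of dose 1 or 2

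*SAP*

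**What the plan says.** SAP 9.3.2 summarises unsolicited AEs by system organ class "and preferred term and treatment group for each vaccination and over all vaccinations". The base for each percentage is stated: "Denominators for percentages are the number of participants who received the vaccination being summarized". The section gives no onset window, no exposure adjustment and no rule for assigning an event to a dose. The only trace of such a rule is the column "Associated with Dose No" in Listing 22 (also in Table 139).

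Collection is continuous. Protocol section 4 says: "Unsolicited AEs will be collected from the time of each study vaccination through 28 days after the last vaccination". SAP 4.5.1 turns this into an end date: "Day 57 for Oral and Sublingual Cohorts, Day 71 for Intradermal Cohorts". SAP 4.4.5 gives the dosing days. For oral: "Cohort A and B participants received 3 doses administered orally in clinic on Day 1, Day 15, and Day 29". For sublingual: "Cohort C and Cohort D received 3 doses administered sublingually in clinic on Day 1, Day 15, and Day 29". Protocol 7.3.2 and 7.3.4 allow ±2 days on each dose interval.

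Solicited events are handled differently: SAP 9.3.1 uses the same seven-day period after every dose. Protocol 11.4.2 asks for per-vaccination summaries of solicited AEs only. The per-vaccination summary of unsolicited AEs is added by the SAP.

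**The concern.** A percentage of people with at least one event depends on how long they were watched. If the watching time differs between doses and the denominator is only a head count, the per-dose percentages differ even when risk does not. The 9.3.2 summary covers all unsolicited AEs, not only those judged related, so it includes the background illness for which a steady hazard is most plausible.

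The primary objective concerns tolerability over three sequential doses. A reader who sees a higher unsolicited AE percentage after dose 3 could take it for worsening tolerability when it reflects a longer observation period.

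**Working it through.** **Check of the plan's own dates.** Third dose plus 28 days: 29 + 28 = 57 for oral and sublingual, and 43 + 28 = 71 for intradermal. Both match SAP 4.5.1.

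**Observation time per dose**, counting each event under the most recent dose:

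- Dose 1: 15 − 1 = 14 days
- Dose 2: 29 − 15 = 14 days
- Dose 3: 57 − 29 = 28 days

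The ratio of dose 3 to dose 1 or 2 is 28/14 = 2.0. Protocol 7.3.2 places the second dose as follows: "This visit is ~14 days after the first dose for oral and SL cohorts", with ±2 days. An interval of 16 days gives 28/16 = 1.75, and one of 12 days gives 28/12 = 2.33.

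**Effect on the percentage.** The documents give no unsolicited AE rate, so the 14-day risk p14 is an assumption, shown over a range. With a constant background hazard and no vaccine effect, p28 = 1 − (1 − p14)², so p28/p14 = 2 − p14.

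| Assumed 14-day risk | Expected after dose 1 or 2 | Expected after dose 3 | Ratio |
|---|---|---|---|
| 5% | 5% | 9.8% | 1.95 |
| 10% | 10% | 19% | 1.90 |
| 20% | 20% | 36% | 1.80 |
| 30% | 30% | 51% | 1.70 |
| 50% | 50% | 75% | 1.50 |

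With 12 vaccinees per cohort (SAP 4.4.3), the 10% row means 12 × 0.10 = 1.2 against 12 × 0.19 = 2.3 participants expected.

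**If doses trigger some events.** Let H = −ln(1 − p14), and let a share s of that hazard be dose-triggered and confined to the first 14 days. Then p28 = 1 − exp(−[H + H(1 − s)]). At p14 = 10% the ratio is 1.90 for s = 0, 1.46 for s = 0.5 and 1.00 for s = 1.

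**After the change.** With the same onset window after each dose, or a rate per person-day, the ratio under a constant hazard is 1.00.

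**Laboratory events.** SAP 3.2.1 includes laboratory AEs among the unsolicited AEs. Protocol 8.2.1 and SAP 9.6 schedule post-baseline safety tests only at Visits 6 and 7, about 7 and 28 days after dose 3. Any AE found by a scheduled test therefore falls under dose 3, and no choice of window makes it comparable with doses 1 and 2.

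**The case against.** Several points on the other side stand.

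- Repeat-dose tolerability is compared formally only for solicited events, which have equal seven-day periods (SAP 9.3.1, Tables 135 to 137). Section 9.3.2 plans no dose-to-dose comparison.
- The unsolicited endpoint runs from first vaccination to 28 days after the last dose. Table 91 has a row for it, unaffected by how events are split by dose.
- No table shell produces the per-vaccination percentages. The shell heading 14.3.1.2 is empty, and Tables 93 and 94 are not split by dose.
- Listing 22 and Table 139 show dose number and days since dose for each event.
- Numbers are small and nothing is tested.

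These limit the consequence but do not remove the problem. The SAP text still commits to the summary, and listings do not correct percentages. Placebo recipients share the same windows, but SAP 4.2 says they are not a comparison group, and there are three per cohort.

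A reader might infer that the dose-3 AE rate is nearly doubled by construction. The documents do not support that. Only the observation time doubles, and a rate per person-day does not change. The percentage nearly doubles only for low-risk background events with a steady hazard.

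A reader might also infer that Cohort E would show falling AE percentages, because SAP 9.7 lists its last vital signs at Day 29, seven days after dose 2. That schedule concerns vital signs. SAP section 15 says the third dose was not given and Visits 6 to 9 were not conducted, but not when AE collection ended. At an assumed 14-day risk of 20%, dose 1 (21 days) gives about 28%. Dose 2 gives about 11% if followed for 7 days but 36% if followed for 28. The direction depends on a fact that the documents do not give.

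**Conclusion.** The point holds for the oral and sublingual cohorts. As written, the per-vaccination percentages for unsolicited AEs are not comparable across doses. The size rests on three assumptions: events are assigned to the most recent dose, the hazard is constant, and the 14-day risk is one of the assumed values. Single preferred-term rows, where risk is likely to be low, lie near the upper end of the ratios shown. The row for any unsolicited AE may lie lower, and dose-triggered events pull the ratio towards 1.

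No direction of bias can be claimed for Cohort E. Neither the primary unsolicited endpoint nor the solicited-event analysis is compromised. This is a cheap improvement to a secondary display.

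**What to change.** In SAP 9.3.2:

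1. State that each unsolicited AE is assigned to the most recent dose before onset.
2. Report the per-vaccination percentages for onset within a common window, no longer than the shortest dose interval or follow-up actually observed in that route. For oral and sublingual this is at most 12 days if the ±2-day visit window is used, since a 14-day window would run past the next dose for some participants. Alternatively, report events per 100 person-days alongside the percentages.
3. Keep the full period, to 28 days after the last dose, for the summary over all vaccinations.
4. Show AEs from scheduled laboratory tests only in that overall summary.
5. For Cohort E, state when AE collection actually ended before choosing its window. SAP 4.5.1 still gives Day 71, which presupposes a third dose.

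The cost is SAP wording and one derived onset-window flag. No existing table shell has to be changed. The downside is that later-onset events appear only in the overall summary and the listings.
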